3.1.2 Secondary Objectives

Our secondary objective is to establish whether cfDNA testing increases the frequency of cancers detected, in particular cancer types with limited detection rates using standard-of-care protocols (e.g., pancreatic cancer, endometrial cancer).

We will also assess patient and provider perceptions about cfDNA testing, and patient-reported outcomes including empowerment, distress, uncertainty, and anxiety.

3.2 Study hypothesis

We hypothesize that testing of cfDNA more frequently than the current imaged-based screening protocols will result in detection of more cancers at earlier stages and improve medical management and quality of life for carriers with HCS.

We also hypothesize that a programmatic approach to cfDNA testing will decrease distress, uncertainty, anxiety and increase quality of life and empowerment among carriers with HCS.

4.0 Study Design

[figure not shown]
4.1 Overall Study Design

We are conducting a randomized control trial to assess the use of cfDNA analysis in cancer surveillance protocols for patients with HCS. We will recruit 1,000 patients across Canada with a known/suspected genetic diagnosis of one of the following HCS: HBOC, LS, NF1, LFS, PALB2, or HDGC that are receiving standard-of-care clinical assessment for cancer by a managing physician under a provincial screening program or cancer surveillance protocol.

The study design is illustrated in Figure 1. At study enrollment, participants will be randomized to a control cohort (n=500) or an experimental cohort (n=500), stratifying for genetic HCS background. All participants in the experimental cohort will provide blood samples tri-annually (every four months) for four years, either at the study hospital, or at a local blood laboratory (e.g., LifeLabs or Dynacare). Whenever possible, patients will have research blood collected at the same time as routine blood collections for clinical purposes, to avoid additional venipunctures. Participants randomized to the control cohort will have the option to donate samples to the CHARM Consortium Biobank, for use in future research. Participants in the control cohort can donate between 1-3 blood samples a year, for the duration of the study.

Participants in both the control and experimental cohorts will continue to receive standard-of-care cancer surveillance according to current guidelines, as they were prior to study enrollment. Blood samples from the experimental cohort will be subject to a

Figure 1. Study Design.

cfDNA sequencing assay, and results will be communicated to participants by the study team. Participants who receive a “positive” cfDNA assay result will be offered follow-up diagnostic procedures to confirm or rule out the presence of a malignancy. The diagnostic investigations are outlined in “Cohort Specific Diagnostic Workflows”, appended to this protocol. If an abnormality is identified by a diagnostic investigation done in follow-up to a “positive” cfDNA assay result, additional investigations (e.g., imaging or biopsy) will be performed as part of the participants clinical care, and will be guided by the participant’s clinical team, or study investigator. All participants will be followed by the study team for a minimum of 5 years, from their first blood collection. To assess the efficacy of the cfDNA assay, we will compare cfDNA assay results to the results of the participants standard of care cancer surveillance results.

Lastly, we will use questionnaires and semi-structured interviews to explore participants’ experiences with cfDNA testing, to understand perceptions of the clinical utility of cfDNA tests for HCS management and identify factors facilitating or impeding the uptake of this test in HCS management and patient decision making.

4.2 Biospecimen Collection

Blood samples may be collected at UHN or in a community laboratory (e.g. LifeLabs or Dynacare). Repeat blood draws may be requested if technical issues with samples preclude sample processing or reporting (e.g., if blood is hemolyzed or collected in the wrong tube). Biospecimen labels will contain a unique study ID, and will not contain any identifying information (including name, DOB, MRN). Participants will be reminded to complete their blood collections by the study team either via phone or email, depending on participant preferences documented at the time of enrollment. We will tell participants that email is not secure, and therefore if they have any questions, they should not send sensitive information via email. Instead, they should email a member of the study team and arrange a phone call.

Hospital Blood Collection

Blood samples may be collected at UHN by either a study team member who has phlebotomy certification, or at the hospital blood collection laboratory. 30mL of blood (3x10mL Streck tubes) will be collected each time. Participants will have research blood work done at the hospital if they have an in-person clinical appointment around the same time as their next scheduled research blood collection, or if they express a preference for blood collection at the hospital over an external laboratory.

Blood collection at off-site blood laboratory

Blood samples may be collected at an external laboratory (LifeLabs or Dynacare). We will not disclose patient names or identifying information directly to Dynacare or LifeLabs. We will either contact patients over phone to obtain verbal consent for phlebotomy using Dynacare/LifeLabs, contact them via email (if they have previously consented to email communication), or speak to the patient during their in-person appointment. Patients will be provided with requisitions for external phlebotomy, which will include PI billing information and a study ID.

If we speak to the participant in-person, we will provide them with the requisition form and tell them they have to directly contact LifeLabs to arrange blood work. If the patient does not live near a LifeLabs location, and would prefer to go to Dynacare, we will provide the patient with a blood collection kit to bring to Dynacare. The kit will include the Dynacare requisition, the blood collection tubes, and packaging/materials to mail the kit back to the study team. The blood collection kit will not contain any personal identifying information.

If we communicate over the phone, following the study SOPs, we will obtain verbal consent from participants to send non-identifying documents to them over email. The external blood requisitions will not contain any personal identifying information. Upon request, we can mail the external blood lab requisition to a participant. If the participant does not live near a LifeLabs, we will mail out a blood collection kit to their home and instruct the participant to bring the kit to Dynacare. Participants will be notified that they will have to directly contact Dynacare or LifeLabs to arrange their blood work and take their requisition form or blood collection kit.

As per LifeLabs storage retention SOP, patient information will be kept as a scanned copy for 7 years. Patient names will not be collected, however, a scanned copy of the requisition form will be retained for tracking purposes. Participants will be verbally informed about this and should they not feel comfortable with this information being provided to Dynacare/LifeLabs, they will not be able to use their services. As per Ontario Dynacare's storage retention SOP, patient information will be kept as a hard copy for 10 years.

Tumour sample collection

If a malignancy is identified in a participant, we may request a tissue sample from the surgery or core biopsy and use it to determine the genetic concordance between tumours and matched blood samples. In addition, for participants with a previous history of cancers, we may request a tissue sample related to the previous malignancy from pathology archives, which will help the researchers to distinguish the mutational signatures associated with the new cancer diagnosis from signals from the other cancers.

This part of the study is optional. Some of the tissue-studies may be funded by the Terry Fox Marathon of Hope Cancer Network (MOHCCN) program. If a participant provides consent for data sharing in controlled access databases, we may share de-identified data (sequencing + clinical data) with the MOHCCN program. This de-identified data is uploaded to an access-restricted database. Only MOHCCN members, who sign joinder agreements and specify how data will be used, can access this data. Furthermore, data cannot be downloaded from the database. If a participant does not provide consent for data sharing in controlled-access databases, the CHARM study team may still sequencing tumour samples (if a participant has provided consent for tumour testing), however data generated from sequencing and associated health data will not be shared with the MOHCCN program. All samples will be collected under this research study. There will not be additional sample collection for MOHCCN only.

Participants will also have the option to donate any leftover tissue sample to the CHARM Consortium Biobank.

A fresh frozen or formalin-fixed paraffin-embedded (FFPE) tissue sample from a surgery or core biopsy may be requested by the study team. Unstained tissue sections for immunohistochemistry may also be requested (up to 15 unstained sections at 7 microns thickness plus 2 hemotoxylin and eosin (H&E)-stained slides).

4.3 Biospecimen Processing

Control Cohort: de-identified blood samples will be transferred to the CHARM Consortium Biobank (CAPCR 23-5772), housed within UHN or OICR for processing into plasma and buffy aliquots and for long storage. Samples will be processed by either a staff member of [name] laboratory, or the OICR Tissue Portal team. Genetic material will be extracted from some samples prior to storage, to better facilitate storage of a large

volume of samples. Blood samples collected from the control cohort may be used for study validation purposes, continued blood test development, or for other future research studies.

Experimental Cohort: de-identified blood samples will be processed (into buffy and plasma components) by either a staff member of [name] laboratory, or the OICR Tissue Portal team. Plasma cfDNA extraction will be completed by the Tissue Portal team, and extracted cfDNA will be submitted to OICR Genomics for sequencing. A buffy coat sample from a single timepoint will also be submitted to OICR Genomics for genomic sequencing. Remaining buffy coat samples, and any left over extracted plasma cfDNA will be stored at OICR until study completion, and then destroyed, unless the patient provides consent to donate leftover samples to the CHARM Consortium Biobank.

Tumour samples: if available and if the patient provides consent to this optional part of the study, tumour samples will be submitted to OICR for nucleic acid extraction and genomic sequencing. With patient consent, unused tumor samples will be stored in the CHARM Consortium Biobank.

4.4 Sequencing Assays

Since the molecular events driving hereditary cancers are known (i.e. the "first hit" is the inherited mutation and a "second hit" somatic mutation is acquired in the remaining wild-type allele), these "second hits" should be detectable in plasma cfDNA. If additional tumour-specific mutations are also identified, these can likewise be used to monitor disease progression via cfDNA analysis. OICR will perform the following tests on samples collected from the experimental cohort:

1. Shallow Whole Genome Sequencing (sWGS) to detect large copy number changes in cfDNA.
2. A targeted panel (the REVOLVE panel), which uses hybrid-capture and ultra-deep sequencing to achieve >20,000X coverage, to detect exon-level copy number alterations and somatic mutations. This can be used to interrogate the sequence of genes involved in cancer pathogenesis (e.g. *TP53*).
3. Methylation analysis with Cell-free Methylated DNA Immunoprecipitation and high-throughput sequencing (cfMeDIP-seq) or Enzymatic methyl sequencing (EM-seq) to reveal the tumour's tissue-of-origin. This involves surveying the epigenetic marks of tumour-derived cfDNA.

sWGS and the REVOLVE panel are clinically validated tests at OICR and will be done as first line tests on all experimental cohort samples. OICR bioinformaticians will analyze the sequencing results and generate a clinical report. Methylation studies (cfMeDIP-seq or EM-seq) will be performed on remaining cfDNA only following a positive sWGS and REVOLVE panel test result. These methylation studies are not clinically validated at OICR, and the generated sequencing data will be transferred to [name]'s laboratory at UHN for analysis.

The sequencing technology used to analyze blood samples (outlined above) may change over the course of the study (e.g., if a more sensitive test becomes clinically available at OICR, for example plasma 30x WGS).

If available, tumour tissue along with a matched buffy coat sample will undergo genomic studies at OICR, including whole-genome and whole-transcriptome sequencing. With a participant's consent for data sharing, these tissue studies may be funded by the Terry Fox Marathon of Hope Cancer Centre Network (MOHCCN) program, and therefore genomic data generated from samples and de-identified health data (demographic factors, cancer risk factors, cancer diagnosis and treatment details) will be shared with the MOHCCN program. The study team will also submit unstained tissue sections for immunohistochemistry.

Any tumour sample (or extracted tumour genetic material) leftover after sequencing studies are completed will be stored with the CHARM Consortium Biobank (if consent by participant is provided) or will be returned to the study team, and destroyed.

4.5 Clinical Reporting

Blood test requisitions will be completed online through the OICR Genomics Requisition Portal by an authorized study team member. The following PHI will be recorded on the requisition form: participant name, date of birth, sex. The OICR requisition will also capture the participant's germline pathogenic variant in their respective HCS gene. The OICR Genomics Requisition Portal retains all PHI in an access-restricted database accessible only to requisitioners (i.e., study team members who will submit the requisition) and ACMG/CCMG licensed Geneticists who will sign out each report. The ACMG/CCMG licensed Geneticists will be part of the study team and will be internal to UHN. No OICR staff member will have access to the PHI submitted to the Requisition Portal.

We aim for the clinical report to be returned to the study investigator within 45 days of sample receipt by OICR, barring holidays and unforeseen circumstances. Clinical reports will be returned electronically, via OICR's online reporting system. Only the study investigator and designated team member will have access to the reporting system. The study team member will log into the OICR Genomics Requisition System and view/download a copy of the clinical report. The clinical report will contain PHI (patient name, DOB) and will be stored by the study team in a password-protected folder on a secure UHN network (UHN Sharepoint), only accessible by delegated study personnel. Per UHN Research Quality Integration's feedback, study clinical reports will be uploaded to EPIC.

4.6 Return of Results and Follow-up Investigations

Results will be communicated to the participant by the study team member as soon as possible, and reasonable attempts will be made by the study team to return results within 2 weeks from the date of report receipt by the study team.

At the time of study enrollment, participants may be provided with an information sheet explaining a “negative” and “positive” test result (please refer to Result Information Sheet). Participants will not be routinely provided a copy of the genetic testing report. However, upon participant request, a copy of the report can be provided. A physical copy (sent by mail, or provided at the time of an in person appointment) or electronic copies (sent via email) may be provided upon request.

Return of “Negative” cfDNA assay test result

A “negative” or “cancer signal not detected” cfDNA assay results will be communicated to participants by the Study Doctor or designated member of the study team via phone. Following result disclosure, the study team member will remind the participant that the cfDNA assay result does not confirm the absence of cancer, and will reinforce the importance of continuing with standard-of-care cancer screening. If after 3 phone call attempts the study team is not able to get in contact with the participant, they will email the participant the result (please see CHARM2 Negative Result Email). A participant will only be emailed if they have already consented to email communication at the time of enrollment.

Return of “Positive” cfDNA assay test result

A “positive” or “cancer signal detected” cfDNA assay results will be communicated to participants by the Study Doctor via phone call or in-person at the time of a clinical appointment. If the Study Doctor is not able to get in contact with the participant by phone, and if they do not have an upcoming in person clinical visit, the study team may email the participant to let them know their result is now available and to arrange a time for a phone call to review the result. Following result disclosure, the Study Doctor will remind the participant that the cfDNA assay result does not confirm the presence of cancer, and that follow-up diagnostic investigations are needed. The site Study Doctor will initiate the work up for the “positive” result.

Participants will be asked to provide an additional blood sample after a “positive” cfDNA result, which will be transferred to OICR and analyzed (in the same methods as outlined earlier). The results of this additional test may not be returned to the participant, and will primarily be used by the study team to correlate with the previous result, and to rule out the possibility of a technical error/lab mix-up. Additionally, some of the blood sample will be used for clinical testing (CBC, tumor markers etc), as indicated in the cohort specific follow-up diagnostic workflows (appended).

The follow-up diagnostic investigations for a “positive” cfDNA test result, for each HCS cohort, are outlined in “Cohort Specific Diagnostic Workflows”, appended to this protocol. These workflows were developed together with clinicians who follow these patient populations. If the above diagnostic investigations do not identify a malignancy, and the participants next scheduled research blood draw result is still “positive”, a PET-CT will be performed as a final step to assess cancer status.

For participants enrolled at UHN, diagnostic investigations will be completed at UHN, whenever possible, or may be arranged at an external site if not offered at UHN. A contract will be signed with any external site used (for example, the Toronto Immune Digestive Health Institute, or In-Common Laboratories). Participants will be informed that if a diagnostic investigation needs to be completed at a non-UHN site, identifying information (including name, date of birth, OHIP number and version code) will be shared with that site.

The Study Doctor may determine that an alternative workup plan is necessary (for example, if a participant underwent relevant diagnostic investigations completed as part of their standard-of-care surveillance shortly before their blood test, a particular investigation is not available or the wait time is too long, or if the patient has any allergies which prevent a particular investigation). Any alternative workup plan will be documented by the study team. A diagnosis of cancer will be documented based on pathologic confirmation, imaging confirmation (if pathologic not possible), or by other clinical confirmation deemed appropriate by the managing clinician.

Participants with a “positive” cfDNA assay result may also have methylation studies completed (either cfMeDIP or EM-seq) on their remaining cfDNA sample at OICR. The methylation tests are not clinically validated at OICR, and the sequencing data will be transferred from OICR back to [name]’s laboratory at UHN and analyzed by a team member. The methylation analysis is exploratory, and therefore the results of the methylation studies may not be returned to the study doctor, if no tissue-of-origin signal is identified. If a tissue-of-origin signal is identified, results may be returned to the study doctor will be correlated with the results of the clinical follow-up investigations completed above. If a tissue of cancer origin is identified using methylation studies, additional targeted diagnostic investigations will ensue, if not done so previously as part of the initial follow-up investigations. Currently, only a methylation signature for breast cancer has been well established. Other methylation signatures are in progress (brain, pancreas, ovary), and may become available over the course of the study.

The CHARM 2 study clinical review committee, composed of study investigators from different study sites, will jointly review challenging cases (e.g. if diagnostic investigations completed in follow-up to a positive cfDNA result are inconclusive). Patient clinical information (including test results, cancer history, images) will be shared with members of this committee, to aid in result interpretation and discussion of best next steps. All information shared will be de-identified. No information will be shared prior to execution of appropriate DTAs.

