Our community, known as the CHARM Consortium (cfDNA in Hereditary And High-Risk Malignancies), was founded in 2018 to address HCS knowledge and delivery gaps through evaluation of blood-based cfDNA testing. Comprised of 8 genetics clinics from 5 Canadian provinces, CHARM is a patient-engaged biobanking and clinical data annotation service, where blood and available tumour samples are collected from HCS carriers at annual screening visits. Analysis of these samples has led to new advancements in cfDNA sequencing that we propose to test with this prospective trial, by evaluating the detection rate of cfDNA sequencing and the clinical benefit gained by following up on detection of early cancer using cfDNA. Specifically, we have demonstrated the use of three technologies to detect early cancer in HCS through analysis of cfDNA in blood plasma: 1) the CHARM gene panel, a targeted sequencing approach that provides in-depth mutational data on a core set of genes frequently mutated in FCS tumours and offered clinically by our program, 2) cell-free methylated DNA immunoprecipitation and high-throughput sequencing (cfMeDIP-seq), which can detect the specific organ from which the cancer-triggering DNA changes arise, and 3) shallow whole genome sequencing (sWGS), which detects accumulated mutations, copy number alterations and DNA fragmentation patterns that occur secondary to the inherited mutation. These results have suggested that integration of mutation, copy number, and functional (methylation or fragmentation) aspects of cfDNA provide the greatest sensitivity for early HCS detection.

In this study, we will enroll 1,000 patients from across Canada's HCS screening programs. Half of the patients will be randomized to have cfDNA analysis with results returned to managing physicians who will follow-up any abnormal cfDNA findings with appropriate clinical imaging and heightened surveillance. At the end of this study, the rate of cancer detection using cfDNA-informed surveillance will be compared with the rate of detection in the cohort of patients who did not receive the result of the cfDNA test but were managed according to current conventional screening programs.

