4.10 Blinding Methods

This study is not blinded.

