4.11 Endpoints

The endpoints of this study are:

1. To assess the performance of the cfDNA assay for cancer detection in patients with HCS, including assay sensitivity, specificity, PPV, and NPV. The test performance endpoint is a diagnosis of cancer and will be assessed at multiple points during the study (at a minimum yearly). Cancer diagnosis will be confirmed by imaging, pathology, or other confirmation deemed appropriate by the treating physician.
2. To assess the time to cancer diagnosis using cfDNA sequencing compared to controls.
3. To assess the detection rate of cancer with no standard-of-care screening available (e.g., pancreatic cancer, endometrial cancer) using cfDNA sequencing.
4. To assess patient reported outcomes (including anxiety, empowerment, distress, risk perception) using validated scales administered before, during, and after the study.

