7.0 Assessment of Efficacy and Safety

There is a possibility that the sequencing tests (sWGS, targeted panel, cfMeDIP) are less sensitive than standard-of-care screening. We will continuously monitor the concordance between cfDNA assay results and standard-of-care surveillance results. Confirmation of a cancer diagnosis will be supported by imaging confirmation, pathologic confirmation, or another form of clinical confirmation deemed appropriate by the study investigator. Yearly, we will evaluate:

- the percentage of cancers found by standard-of-care screening missed by the cfDNA assay.
- the percentage of positive cfDNA results where no cancer is detected on any follow-up diagnostic investigations.

If we determine that one of the tests are consistently underperforming (e.g. if 50% of cancers found by standard of care screening are missed by cfDNA assay), we will consider discontinuing the underperforming assay, and replacing it with an alternative validated test (e.g. plasma WGS). If we change one or more of the assays over the course of the study, participants will be notified of this change verbally by a study team member. If no alternative test is available, we may decide to end the study early.

The Study Doctor will perform the following tasks to ensure the safety of subjects and the good conduct of the study, on a monthly basis:

- Review the study binder to ensure all documents and communications are up to date
- Review the Inclusion/Exclusion forms for completeness and compliance to study protocol
- Monitor the accrual rate and recruiting efforts
- Monitor the number of ‘false positive’ results, and the number of subsequent diagnostic investigations undergone by the participant
- Monitor participant compliance to routine cancer screening protocols

Study related adverse events will be documented and reported to the UHN REB, as per the standard institutional procedure.

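### In an unblinded trial, a cancer event may rest on confirmation with no stated criteria, by roles that differ between sections, which can bias the detection and accuracy results

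*Protocol*

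**What the plan says.** The Protocol states the confirmation rule for a cancer diagnosis three times.

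- **Section 4.6:** pathology; imaging if pathology is not possible; "or by other clinical confirmation deemed appropriate by the managing clinician".
- **Section 4.11 (Endpoints):** "Cancer diagnosis will be confirmed by imaging, pathology, or other confirmation deemed appropriate by the treating physician".
- **Section 7.0:** imaging, pathology, or "another form of clinical confirmation deemed appropriate by the study investigator".

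None of the three gives criteria for the last route. Section 8.0 adds that predictive values are judged against clinical testing, with an open-ended list that includes protein biomarkers.

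On who knows what, section 4.10 states "This study is not blinded". Section 2.1 describes "results returned to managing physicians who will follow-up any abnormal cfDNA findings", and section 4.5 says that "study clinical reports will be uploaded to EPIC".

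The only review body is the clinical review committee in section 4.6. It consists of study investigators who "will jointly review challenging cases". They receive de-identified information that includes test results, to help with interpretation and next steps.

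**The concern.** A cancer diagnosis is the event behind most of the trial's results. It is the reference standard for sensitivity, specificity, PPV and NPV (4.11, endpoint 1), the event for time to diagnosis (endpoint 2), and the count in the between-arm detection rate (8.0), on which the power statement is based.

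If the event can be declared on judgement alone, by someone who can know both the arm and the cfDNA result, two things can go wrong.

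- **Between arms.** Work-up after a positive cfDNA result happens only in the experimental arm. Equivocal findings are therefore more likely there, and accepting some of them as cancers raises that arm's count and shortens its time to diagnosis.
- **Assay accuracy.** Nothing in the rule stops a positive or repeat-positive cfDNA result from being part of the confirmation. A false positive could then be recorded as a true positive, which raises PPV and sensitivity.

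Both errors favour cfDNA testing. They are also hard to undo later unless the route of confirmation was recorded at the time of diagnosis.

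**Working it through.** **1. The three statements side by side**

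| Section | Order of evidence | Who judges the open route | Criteria for it |
|---|---|---|---|
| 4.6 | Pathology, then imaging if pathology not possible, then other | Managing clinician | None |
| 4.11 | Imaging, pathology or other; no order | Treating physician | None |
| 7.0 | Imaging, pathology or other; no order | Study investigator | None |

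Managing clinician and treating physician may be the same person. The study investigator need not be. So there are at least two deciding roles, and the sections disagree on whether pathology comes first.

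**2. Inputs for an illustration of size**

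- 500 per arm (Protocol Summary; 4.1).
- 5% detection rate without cfDNA at the end of the study, a 2-point increase as target, two-sided 0.05 (8.0).
- Up to about 5-10% of the experimental arm testing positive each year (6.0), so 0.05 × 500 = 25 to 0.10 × 500 = 50 participants.
- Number of diagnoses by the open route: not given. I call the excess in the experimental arm *x* and treat it as an assumption.

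The protocol has no figure of its own on this point. The power figure in 8.0 (above 97% for a 2-point increase) does not reproduce: 5% v 7% with 500 per arm gives 26.5%. That is a separate matter, and nothing below depends on it. The protocol also names no test for the detection rate, so the uncorrected chi-square test is my assumption.

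**3. Chance of a significant result when there is no true difference**

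Control count C ~ Binomial(500, 0.05). Experimental count E ~ Binomial(500, 0.05) + *x*. The test rejects when

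|E − C| / 500 ÷ √[ p̄(1 − p̄) × 2/500 ] > 1.96, with p̄ = (E + C)/1000.

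Summing the exact binomial probabilities:

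| x | x / 500 | Chance of p < 0.05 |
|---|---|---|
| 0 | 0% | 4.9% |
| 5 | 1.0% | 9.5% |
| 7 | 1.4% | 14.3% |
| 10 | 2.0% | 24.7% |

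If the excess is instead modelled as a shift in the experimental rate to 0.05 + *x*/500, the figures for *x* = 5, 7 and 10 are 10.4%, 15.6% and 26.2%. Ten cases equal the whole target effect (0.02 × 500 = 10).

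**4. Single tables, two-sided Fisher exact test, 500 per arm**

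| Control v experimental | p |
|---|---|
| 25 v 32 | 0.41 |
| 25 v 35 | 0.23 |
| 25 v 40 | 0.072 |
| 25 v 42 | 0.042 |

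Starting from equal counts of 25 v 25, it takes 17 extra cases (17/500 = 3.4%) to reach 25 v 42. With uncorrected chi-square, 25 v 41 already gives p = 0.042.

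**5. PPV and sensitivity**

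PPV = (true positives + relabelled) / positives. Five relabelled cases in a year add 5/50 = 10 to 5/25 = 20 percentage points. With an assumed 5 true positives, PPV goes from 5/25 = 20% to 10/25 = 40%, or from 5/50 = 10% to 10/50 = 20%. Sensitivity becomes (TP + u)/(TP + u + FN) for *u* relabelled cases, and this rises with *u* whenever any cancer was missed.

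**The case against.** Several points on the other side are sound.

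- **The rule has limits.** Section 4.6 puts pathology ahead of imaging. It provides for cohort-specific work-ups, a PET-CT if the next scheduled draw is still positive, and committee review of difficult cases. Section 4.13.1 describes a false positive as one where no follow-up investigation finds cancer, which constrains relabelling. The work-up appendix is not shown and may say more. These limits reduce the problem. They do not remove it: 4.11 drops the order, the committee is described neither as blinded nor as an endpoint adjudicator, and its example case (an inconclusive work-up after a positive result) can arise only in the experimental arm.
- **The role mismatch is partly verbal.** Two of the three titles can mean one person, and the third appears in the section on yearly assay monitoring. This stands, and it makes that part a harmonisation edit.
- **Knowledge of the result is intrinsic.** Returning results is the intervention, and extra work-up in one arm follows from it. No endpoint definition can change that.
- **Adjudication detail may sit in an SAP or charter.** That is so for procedures. But the protocol itself fixes who decides and on what basis, and does so inconsistently.

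A reader might infer that about seven soft diagnoses would turn a null result into a significant one, since 25 v 35 gives Fisher p = 0.23 and 25 v 42 gives 0.042. The documents do not support this. The pair 25 v 35 is the plan's own 2-point effect, not a null. From 25 v 25, seven extra cases give p = 0.41. A reader might also infer that soft diagnoses will accumulate in the experimental arm. The protocol shows only that they can.

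**Conclusion.** The concern holds as a possible bias of unknown size. As written, a cancer event may rest on confirmation without criteria, judged by someone who can know the arm and the cfDNA result. The sections also disagree on the deciding role and on whether pathology comes before imaging. The likely direction is towards more and earlier diagnoses in the experimental arm, and towards higher PPV and sensitivity.

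The percentages in the working show scale only. They rest on assumed counts, an end-of-study rate of 5% in both arms, and a chi-square test that the protocol does not specify. It should not be said that the rule does bias the results, or that a given handful of cases would decide the trial. The change is worth making, because the avoidable part of the problem is cheap to remove.

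**What to change.** 1. Use one endpoint definition and one deciding role in sections 4.6, 4.11 and 7.0, and have 8.0 refer to it.
2. Record the route of confirmation (pathology, imaging, other) for every cancer in both arms.
3. In the main analysis, count cancers confirmed by pathology, or by imaging where pathology is not possible. This is the order already in 4.6.
4. State that a cfDNA result cannot itself serve as confirmation.
5. Add the cases confirmed by any other route, from both arms, in a sensitivity analysis.

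The committee could also classify the cases in item 5 with arm and cfDNA result removed. That is optional: an off-cycle work-up or PET-CT may reveal the arm, the members are study investigators, and data sharing between sites awaits agreements.

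The cost is revised wording, one data field and one extra analysis, with no change to patient care. The downside is that a few true but unconfirmed cancers leave the main count. None of this removes the effect of extra work-up in one arm, which should be acknowledged when the results are interpreted.
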